Subjects will be followed until the last subject enrolled has completed the 1 year follow-up visit or until PMA approval is obtained in the US (whatever is later), however, Medtronic will work with FDA to determine if longer term follow after PMA approval is required. A post-approval analysis of 1-year Major Device Event (MDE) rate is planned.

6. Determination of Sample Size

One hundred (100) enrolled subjects will ensure 87 evaluable subjects at 30 days. The primary endpoint analysis will be completed upon 87 evaluable subjects reaching the 30 day endpoint. Based on Valor II study results, Valiant Evo is expected to perform similarly and have 6% of MDE combined with access and/or deployment failures at 30 days. The sample size of 87 evaluable subjects will provide 85% statistical power for the study hypothesis. The type I error is controlled at the one-sided 0.025 level.

Table 1: Power Analysis

True rate of MDEs combined with access and/or deployment failures at 30 day with Valiant Evo	6%
Performance Goal	16%
Significance level	0.025
Statistical test	One-sided binomial test
Evaluable sample size	n=87
Enrollment	Minimum of 100 subjects enrolled to ensure 87 evaluable subjects
Statistical power from the 87 evaluable subjects	85%

One hundred (100) enrolled subjects will also ensure 63 evaluable subjects at 1-year on MDE rate for the post-approval analysis. The VALOR II study with the Valiant stent graft system enrolled 160 patients with DTAA and was assessed through 12 months for purposes of PMA (P100040) approval. Through 1-year post-

treatment, the rate of MDEs combined with access and/or deployment failures was 7.1% (11/153) (Medtronic internal data using the Valiant Evo proposed definition). Therefore, for the purpose of post approval analysis, the rate of MDEs combined with access and deployment failures at 1-year with Valiant Evo is estimated to be 7.1% (refer to Table 22 below for power analysis assumptions).

Table 2: Power Analysis for Post-approval Analysis of 1-year Endpoint

Estimated rate of MDEs combined with access and/or deployment failures at 1 year with Valiant Evo	7.1%
Performance Goal (PG) at 1-year	20%
Significance level	0.05
Statistical test	One-sided binomial test
Evaluable sample size	N = 63 at 1 year
Enrollment	IDE cohort will enroll a minimum of 100 subjects and is expected to have a minimum of 63 evaluable subjects at 1-year follow up.

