Statistical power from 63 or more evaluable subjects	92% (overall study power for passing both hypotheses is 81%)

7. Statistical Methods

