7.9. Evaluation of Objectives

Primary Endpoint

The primary objective will be assessed by the composite safety and effectiveness endpoint that is based on the proportion of subjects who experienced:

- (a) Access and/or deployment failures; and/or
- (b) Major device effects (MDE) within 30 days post index procedure

MDEs include the occurrence of any of the following:

- Device-related secondary procedures
- Device-related mortality
- Conversion to open surgery
- Thoracic aortic aneurysm rupture

Detailed definitions of MDEs are defined in Clinical Investigational Plan Appendix L.5.

The primary study endpoint will be tested against a performance goal of 16% at 30 days:

$$H_0: p \geq 16\% \text{ vs. } H_a: p < 16\%,$$

where p denotes the true event rate of primary study endpoint in the target population. If the null hypothesis

(H₀) is rejected at the one-sided 0.025 statistical significance level, it is considered that the performance goal for the primary endpoint has been reached.

The analysis set of all enrolled subjects will be used for the analysis. The primary study endpoint is a dichotomous study outcome; hence, an exact method based on the binomial distribution will be used for the hypothesis testing.

Primary Endpoint Calculation:

A subject will be a failure on the primary endpoint if the subject either failed on access/deployment or had an MDE within 30 days. A subject will be a success on the primary endpoint if the subject is confirmed for access and deployment success as well as free from MDE. The failure rate of the primary endpoint is the percent of failures in all the evaluable subjects for the endpoint, i.e., in total number of failures and successes. Note that a subject who had an MDE within 30 days is one of the subjects in m as defined below. A subject who is free from MDE is one of the subjects in k as defined below.

MDE Rate Calculation:

All MDEs will be adjudicated by the Clinical Event Committee (CEC) per study protocol. MDE rate will be calculated as follows (Table 5):

Table 5: MDE Rate Calculation:

MDE rate = $m/(m + k)$	Within 30 Days	Within 183 Days	Within 365 Days
m = No. of Subjects Who Had MDE(s)	No. of subjects who had at least one MDE with onset day from Day 0 to Day 30, inclusive.	No. of subjects who had at least one MDE with onset day from Day 0 to Day 183, inclusive.	No. of subjects who had at least one MDE with onset day from Day 0 to Day 365, inclusive.

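### SAP Table 2's 92% power is not a floor for 63 or more evaluable subjects, and Table 1's 85% holds at 87 while the tested number is left open between 87 and 100

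*SAP*

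**What the plan says.** The figures are in SAP Section 6, which plans the pooled US and International analysis. They do not concern the International protocol's own 47-subject analysis, which is descriptive.

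**1-year test (Table 2).** Performance goal 20%, estimated rate 7.1%, significance level 0.05, one-sided binomial test, with 63 evaluable subjects as the expected minimum. The power row is labelled "Statistical power from 63 or more evaluable subjects", and its entry begins "92% (overall study power for passing both hypotheses is 81" (per cent).

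**30-day test (Table 1 and text).** True rate 6%, performance goal 16%, n = 87. The text says "The sample size of 87 evaluable subjects will provide 85% statistical power for the study hypothesis". On enrolment, Table 1 says "Minimum of 100 subjects enrolled to ensure 87 evaluable subjects". Section 6 adds "The type I error is controlled at the one-sided 0.025 level", and Section 7.9 states that "an exact method based on the binomial distribution will be used for the hypothesis testing".

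**Which subjects enter the 30-day test.** Sections 5 and 6 say the analysis is done once 87 evaluable subjects have reached 30 days, and Section 5 says the data from those 87 support the submission. Section 7.9 uses the analysis set of all enrolled subjects, with every evaluable subject in the denominator. Table 5 in that section counts a subject without an MDE after only one day in study.

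**The concern.** For an exact binomial test the permitted number of failures is a whole number that rises only at certain sample sizes. Between those sizes, each added subject makes the same failure count more likely to be exceeded, so power drifts down until the next jump. Both planned numbers, 63 and 87, sit exactly on a jump. They are the most favourable points of their stretch, and the next few larger numbers have less power.

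This matters in two ways. Table 2 attaches its power to an open-ended range, so the reader takes 92% as a minimum. Table 1 gives its power at one number, but other parts of the SAP allow a larger number to be tested without saying what happens to power there. The 81% joint figure depends on both tests.

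**Working it through.** **Inputs.** 30 days: p0 = 0.16, p1 = 0.06, alpha = 0.025 (SAP Table 1 and Section 7.9). 1 year: p0 = 0.20, p1 = 0.071, alpha = 0.05 (SAP Table 2). Both tests are one-sided and exact.

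**Formula.** For each n, the critical count c is the largest integer with P(X ≤ c | n, p0) ≤ alpha. Power is P(X ≤ c | n, p1).

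**Reproducing the plan's figures.**
- 1 year, n = 63: P(X ≤ 7 | 63, 0.20) = 0.0473 and P(X ≤ 8 | 63, 0.20) = 0.0937, so c = 7. Power = P(X ≤ 7 | 63, 0.071) = 92.3%. Stated: 92%.
- 30 days, n = 87: P(X ≤ 7 | 87, 0.16) = 0.0233 and P(X ≤ 8 | 87, 0.16) = 0.0495, so c = 7. Power = P(X ≤ 7 | 87, 0.06) = 84.9%. Stated: 85%.

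Both agree to the whole percentage at the stated n.

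**1 year, 63 upward.**

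| n | c | Size at 20% | Power at 7.1% |
|---|---|---|---|
| 63 | 7 | 0.0473 | 92.3% |
| 64 | 7 | 0.0420 | 91.7% |
| 65 | 7 | 0.0373 | 91.1% |
| 66 | 7 | 0.0330 | 90.5% |
| 67 | 7 | 0.0292 | 89.9% |
| 68 | 7 | 0.0258 | 89.2% |
| 69 | 8 | 0.0490 | 94.5% |
| 75 | 8 | 0.0243 | 91.6% |
| 76 | 9 | 0.0450 | 95.8% |

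From 76 on, power is at least 93.9% (reached at 81). Rounded to whole percentages as in Table 2, 64 and 75 still read 92%. The values at 65 to 68 do not. The largest gap from the stated figure is 92 − 89.2 = 2.8 points. With the unrounded source rate, 11/153 = 7.19%, power is 91.9% at 63 and 88.6% at 68.

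**30 days, 87 to 100.**

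| n | c | Size at 16% | Power at 6% |
|---|---|---|---|
| 87 | 7 | 0.0233 | 84.9% |
| 88 | 7 | 0.0211 | 84.2% |
| 90 | 7 | 0.0173 | 82.8% |
| 92 | 7 | 0.0141 | 81.3% |
| 93 | 7 | 0.0128 | 80.5% |
| 94 | 7 | 0.0115 | 79.7% |
| 95 | 8 | 0.0239 | 88.3% |
| 100 | 8 | 0.0147 | 85.4% |

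The low point is at 94, where the gap is 85 − 79.7 = 5.3 points. With the protocol's predicate rate of 9/160 (5.6%) in place of 6%, the shape is the same but higher: 88.4% at 87 and 84.1% at 94.

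**Joint power.** The chance of passing both tests cannot exceed the chance of passing either one, whatever the correlation. At n = 87 the 30-day power of 84.9% leaves room for 81%. At n = 93 the ceiling is 80.5%, and at n = 94 it is 79.7%. The ceiling at 93 would print as 81% after rounding, but it is reached only if every trial that passes at 30 days also passes at 1 year.

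**The case against.** The strongest reply is that both stated powers are right at their stated numbers, and that a sawtooth is a property of every exact binomial design. That stands. It answers any charge that the sample-size arithmetic is wrong at 63 or 87.

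On Table 2, the shortfall covers four sample sizes, is under 3 points, and concerns a post-approval analysis. That also stands, and it limits the size of the point. It does not rescue the row label, which gives a range and is wrong within it, just above the planned minimum.

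On Table 1, a reader might infer that the SAP promises 85% for any number from 87 up. It does not: the table gives n = 87, and the word minimum applies to enrolment. Sections 5 and 6 also tie the analysis to 87. If exactly 87 are tested, Table 1 needs no correction. If nearly all of 100 are tested, which the one-day rule in Table 5 makes plausible, power is again 85% or better. Only 88 to 94 falls short, and nothing in the documents shows that this band is likely. What remains is that Section 7.9 does not restrict the test to 87, so the SAP has not excluded the band.

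**Conclusion.** The point holds for Table 2 as a wrong statement, and for Table 1 as an unresolved ambiguity.

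- **Table 2.** 92% is not a floor for 63 or more. It fails at 65 to 68, with a minimum of 89.2%, on the SAP's own inputs.
- **Table 1.** 85% is correct at 87. The SAP leaves the tested number open between 87 and 100, where power runs from 79.7% to 88.3%.
- **Joint figure.** 81% is not shown to be wrong at the planned 87 and 63. It is out of reach if 93 or 94 subjects are tested at 30 days, subject to the rounding remark for 93. The SAP does not say how it was derived, so the effect of the 1-year dip on it cannot be worked out.

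A reader might also infer that the false-positive rate is at risk. It is not: the exact size stays below alpha at every n, and it is lowest within each stretch where power is lowest.

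These results assume the stated true rates (6% and 7.1%) and a critical count set from the number actually tested. The 30-day range takes 100 as the upper limit. Table 1 calls 100 a minimum, and at 101 and 102 power would be 84.7% and 84.1%.

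**What to change.** 1. In Table 2, restate the power as 92% at exactly 63 evaluable subjects and at least 89% for 63 or more.
2. In Table 1, label the 85% as holding at n = 87.
3. Reconcile Sections 5 and 6 with Section 7.9. Say whether the primary test uses the first 87 evaluable subjects, and if so how they are identified and how later subjects are reported, or all evaluable subjects among those enrolled.
4. If the number may exceed 87, give the 30-day power as a range of about 80% to 88% over 87 to 100.
5. State the evaluable numbers and the dependence assumption behind the 81%. If more than 87 may be tested, note that it does not hold across the whole range.

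The cost is a few edited lines and slightly less favourable figures. No patients are added, and the hypotheses, performance goals and significance levels do not change. The choice in step 3 should be made before the 30-day outcomes are reviewed.

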7.1. Study Subjects

7.1.1. Disposition of Subjects

Summaries of subject accountability will be created for subjects enrolled in the US Clinical Trial and the International Clinical Trial as well as two cohorts combined. Subjects discontinued or dropped off from the study will be listed by last day in study and reason for discontinuation.

7.1.2. Clinical Investigation Plan (CIP) Deviations

Clinical Investigation Plan (CIP) deviations will be reported and summarized. Major deviations will include violation of informed consent and/or inclusion/exclusion criteria.

7.1.3. Analysis Sets

Analysis set to be used for each endpoint analysis will consist of all subjects who were enrolled. The subject will only be considered enrolled when arterial access is established and an attempt to introduce the Valiant Evo Thoracic Stent Graft is made.

7.2. General Methodology

In general, qualitative parameters will be described by their distribution frequencies; quantitative parameters will be described by their mean, standard deviation, minimum, maximum, median, and number of subjects with assessable data.

For events such as adverse events (AE), deaths and secondary procedures, that can occur or are observed at any time during the study, no time window will be applied. For such events, an event that occurs “within 1 month or 30 days” is an event that takes place between Days 0 to 30, inclusive. Similarly, an event that occurs “within 12 months or 365 days” is an event occurring between Day 0 to Day 365, inclusive. Date of event onset will be used to determine when the event occurred. Day 0 is referring to the day of index procedure.

For image-based assessments, such as stent-graft endoleak, patency, and other observations, the following time windows will be applied for by-visit data summaries:

Table 3: Time Windows for Statistical Analyses

Study Visit	Target Day	Time Window
Implant	Day 0	Day 0
1 Month	Day 30	1 – 90 days
6 Months	Day 183	91 – 304 days
12 Months	Day 365	305 – 548 days
24 Months	Day 730	549 – 913 days
36 Months	Day 1095	914 – 1278 days
48 Months	Day 1460	1279 – 1643 Days
60 Months	Day 1825	1644 – 2009 days

Unless otherwise specified, if different type of images are used and have different finding in the same time window, the imaging technique and sensitivity matrix (CIP Appendix L.3, also see Table 4 below) will be applied. Finding from higher visibility image will be used for analysis. If there are two or more assessments in the same time window, then the assessment closest to the target day will be used in the analysis of event rate at a given time point.

Table 4: Imaging Matrix

Anatomy/Stent Graft Issue Detected	CT with contrast	CT without contrast	MRI with contrast	MRI without contrast	Angiogram/, Aortogram, and Arteriogram
Diameter and Length	1	2	1	2	3
Stent graft migration	1	2	1	2	2-3
Stent graft fracture	2	3	2	3	2-3
Stent graft kinking	2	3	2	3	2-3
Collapse of stent graft	2	3	2	3	2-3
Stent graft twisting	2	3	2	3	2-3
Stent graft patency	1	4	1	4	2-3
Endoleaks	1	4	1	4	2-3
False lumen perfusion	1	4	1	4	2-3
Occlusion	1	4	1	4	2-3
Stenosis	1	4	1	4	2-3
Stent Graft Fabric Defect	1	4	1	4	2-3
1= Highly visible 2 = visible 3 = Not very visible (potential artifacts) 4 = Invisible					

Statistical analyses for this study will be performed using the Statistical Analysis System (SAS) for Windows (Version 9.1 or higher) or other widely-accepted statistical or graphical software.

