	
related aneurysm rupture (i.e., perforation of the aneurysm during the course of the implantation procedure) or as a late aneurysm rupture that follows device deployment.
 
Excluded are aneurysms in anatomic areas other than the targeted segment treated by the Valiant Evo Thoracic Stent Graft System.

Aneurysm expansion	Aneurysm maximum diameter increase > 5 mm as compared to the 1- month contrast enhanced imaging measurements
Stent graft migration	
Evidence of proximal or distal movement of the stent graft (>10 mm) relative to fixed anatomic landmarks (e.g. supra aortic trunks, coeliac trunk), which is not due to remodeling of the subject's vasculature.
 
The 1-month imaging will be used as the baseline for this determination.

Loss of stent graft patency	Defined as a 100% complete blockage (occlusion) of the lumen diameter of any implanted stent graft component(s) as evidenced by CT, angiography, ultrasound, or other appropriate imaging modality, and/or operative pathological analysis.
Endoleak	
Defined by the presence of contrast-enhanced blood outside the lumen of the endoluminal graft but within the aneurysm sac. Endoleaks are classified as follows:
 
Type I a – Leak at the proximal graft attachment site
 
Type I b - Leak at the distal graft attachment site.
 
Type I c - Leak around a fenestration, branch end point, or branch occluding plug (e.g., plug occluding a subclavian artery or iliac artery to prevent flow into an aneurysm sac).
 
Type II – Retrograde flow from branch arteries arising from the excluded segment.
 
Type III a – Endoleak between the segments of the modular graft (junctional endoleak).
 
Type III b – Endoleak in the mid-graft region due to the defect of fabric.
 
Type IV – Transgraft leak due to fabric porosity.
 
Type V – Aneurysm enlargement in the absence of any demonstrable perfusion of the aneurysmal sac
 
Type undetermined - Endoleak of undefined origin

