m = No. of Subjects Who Had Event(s)	No. of subjects who had an event with scan day within the 1-month window.	No. of subjects who had an event with scan day within the 6-month window.	No. of subjects who had an event with scan day within the 12-month window.
n = No. of Subjects Who Had Readable Images	No. of subjects who had a readable image within the 1-month window.	No. of subjects who had a readable image within the 6-month window.	No. of subjects who had a readable image within the 12-month window.
Event rate = m/n	Through 1 Month	Through 6 Months	Through 12 Months
m = No. of Subjects Who Had Event(s)	No. of subjects who had an event with scan day within the 1-month window.	No. of subjects who had an event with scan day within 1- or 6-month windows.	No. of subjects who had an event with scan day within 1-, 6- or 12-month windows.
n = No. of Subjects Who Had Readable Images	No. of subjects who had a readable image within the 1-month window.	No. of subjects who had an event (counted in m) or had a readable image within the 6-month window.	No. of subjects who had an event (counted in m) or had a readable image within the 12-month window.

The imaging based event rates by visit at 24, 36, 48 and 60 months will be calculated in a similar way as above; i.e., m = number of subjects who had an event with scan day within the statistical analysis window of the specific time point; n = number of subjects who had a readable image within the 12-month window.

The cumulative event rate through 24, 36, 48 and 60 months will be estimated using survival analysis. Kaplan-Meier estimates, along with its standard error using the Greenwood method, will be reported for non-image based events. The image-based events are interval censored data and the interval censored survival analysis method will be used to calculate the event rates.

When reporting the site reported endoleaks, both site imaging findings and the events treated during secondary procedures will be accounted for in the analysis.

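### SAP 7.2 ranks discordant images in one window by visibility without regard to scan date and gives no precedence over its closest-to-target rule, so a clear CT can displace a later angiographic occlusion nearer the target day

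*SAP*

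**What the plan says.** SAP 7.2 assigns images to the Table 3 analysis windows and then gives two selection rules in succession.

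- **Visibility rule.** It applies "if different type of images are used and have different finding in the same time window" and refers to the Table 4 matrix: "Finding from higher visibility image will be used for analysis". It opens with a general carve-out for anything specified otherwise. Scan date is not mentioned.
- **Date rule.** If a window holds two or more assessments, "then the assessment closest to the target day will be used in the analysis of event rate at a given time point".

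In Table 4 the columns are contrast CT, non-contrast CT, contrast MRI, non-contrast MRI and angiography, and 1 is the best score. The occlusion row reads "Occlusion 1 4 1 4 2-3" and the endoleak row "Endoleaks 1 4 1 4 2-3". The patency row has the same scores. Ultrasound has no column.

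Protocol H.1 contains the date rule only. Protocol L.2.1 defines loss of patency as complete occlusion "as evidenced by CT, angiography, ultrasound, or other appropriate imaging modality", or by operative pathology.

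SAP 7.9, Table 6, gives separate formulas for rates at a visit and rates through a visit. The numerator through 12 months is "No. of subjects who had an event with scan day within 1-, 6- or 12-month windows". SAP 7.9 also says that the site-reported endoleak analysis takes account of endoleaks treated at secondary procedures.

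**The concern.** A visibility ranking is sound for two looks at the same state of the graft: if CT and angiography a few days apart disagree, trust the better technique. It is not sound for two looks weeks or months apart, because the later image may show a new event, or the result of treatment. The two images then do not conflict, and preferring the sharper one discards a true observation.

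Because the visibility rule has no date condition and no stated place relative to the date rule, two programmers could derive different rates from the same scans. One of those rates could leave out an occlusion that meets the protocol's own definition. Occlusion of a stent graft is a device failure for which each case counts.

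**Working it through.** No sample size, power or alpha figure in either document depends on this rule, so there is no stated figure to reproduce. The check applies both rules to example scan pairs.

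**Window widths (SAP Table 3), last day − first day + 1:**

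- 1 month: 90 − 1 + 1 = 90 days
- 6 months: 304 − 91 + 1 = 214 days
- 12 months: 548 − 305 + 1 = 244 days
- 24 months: 913 − 549 + 1 = 365 days; 36 and 48 months are also 365
- 60 months: 2009 − 1644 + 1 = 366 days

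After a CT on the target day the window stays open for a further 60 days (1 month: 90 − 30), 121 days (6 months: 304 − 183), 183 days (12 to 48 months, e.g. 548 − 365) or 184 days (60 months: 2009 − 1825). That is long enough for a new event.

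**Rules applied.** Contrast CT scores 1 and angiography 2-3, so the visibility rule always keeps the CT. The date rule keeps the image with the smaller |scan day − target day|.

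| Window (target) | Contrast CT | Angiogram | CT distance | Angiogram distance | Visibility rule | Date rule |
|---|---|---|---|---|---|---|
| 12 months (365) | Day 310, clear | Day 360, occluded | 55 | 5 | clear | occluded |
| 12 months (365) | Day 310, occluded | Day 360, clear | 55 | 5 | occluded | clear |
| 1 month (30) | Day 15, clear | Day 40, occluded | 15 | 10 | clear | occluded |
| 12 months (365) | Day 310, clear | Day 500, occluded | 55 | 135 | clear | clear |
| 12 months (365) | Day 365, clear | Day 500, occluded | 0 | 135 | clear | clear |
| 1 month (30) | Day 30, clear | Day 70, occluded | 0 | 40 | clear | clear |

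**When the rules diverge.** For a CT on Day c before target t, a later angiogram on Day g is nearer the target when g < 2t − c. With c = 310 and t = 365, 2 × 365 − 310 = 420, so the rules disagree for angiograms on Days 311 to 419. A CT on Day 310 lies within the protocol's 12-month visit window (Days 305 to 425), so the example does not need an off-schedule CT. If the CT falls on or after the target day, a later angiogram is never nearer and both rules keep the CT.

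**Size of one case.** One subject moves a rate by 1/n: 1/47 = 2.1 points, 1/87 = 1.1 points, 1/100 = 1.0 point. These n are illustrative. The Table 6 denominator is subjects with readable images, and that number is not given.

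**The case against.** Several points on the other side narrow the matter, and most of them stand.

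- **A finding late in the window.** With a clear CT on Day 310 and an occlusion on Day 500, the date rule also keeps the CT. A reader might blame the visibility rule for that loss, but changing it alone would not alter the rate at 12 months. The rules part only when the later image is nearer the target.
- **One-directional bias.** A reader might infer that the rule always removes failures. It is symmetric: an earlier positive CT is kept over a later clear angiogram. The documents show no net direction.
- **The cumulative rows.** A reader might infer that the Table 6 through-visit rates are also affected. SAP 7.2 introduces the windows for by-visit summaries, and the Table 6 wording can be read as already counting any positive image. Cumulative image-based rates through 24 to 60 months use interval-censored methods. What remains is ambiguity: the visibility sentence, unlike the date sentence, is not limited to rates at a time point, and Table 6 does not say whether selection precedes counting.
- **Endoleak.** SAP 7.9 restores treated endoleaks in the site-reported analysis. In the core-lab analysis the issue arises only if the angiogram was sent and read; Protocol F.3 sends procedural and interim images only when further analysis is needed. A reader might infer that the core-lab result should therefore also take in operative findings. The documents do not require that, and an independent image reading can reasonably stand alone.
- **L.2.1.** It lists acceptable evidence, whereas 7.2 is a tie-break, and an angiogram with no discordant scan still counts. This is fair, but a tie-break should not remove a later finding that meets the definition.
- **An unseen source.** The SAP names the US trial's protocol as its primary resource and cites a protocol Appendix L.3 for the matrix. In the supplied Protocol, L.3 is the follow-up extension. A limit in the cited appendix cannot be ruled out, but the SAP states none.

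**Conclusion.** The defect is real but limited. As written, the visibility rule ignores scan date, its order relative to the next sentence is unstated, and for some scan pairs it gives a different answer from Protocol H.1. It can therefore produce a wrong image-based rate in either direction, chiefly for loss of patency and for endoleaks outside the treated-endoleak provision of SAP 7.9.

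The 30-day primary endpoint, secondary procedures, adverse events and MDEs are unaffected: they are not selected by image and are counted by onset. The affected endpoints are descriptive. One subject shifts a rate by 1.0 to 2.1 points over the illustrative denominators of 100 to 47. How many subjects would have such a scan pair cannot be derived from the documents, so no total effect is claimed.

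The conclusion rests on reading SAP 7.2 as it stands, with no limit supplied by the appendix it cites.

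**What to change.** In SAP 7.2 and 7.9:

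1. Apply the Table 4 ranking only to images taken within a pre-specified interval of each other, with no intervening procedure.
2. Treat all other images as successive observations, and use the closest-to-target rule for rates at a visit, as in Protocol H.1.
3. State this order of precedence.
4. State that the Table 6 through-visit rows, and loss of patency within 12 months, count any image in the relevant windows that meets L.2.1, before any selection under 7.2.

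The cost is a few sentences of SAP text and a small change to the derivation program. Some reported rates may become slightly less favourable. An occlusion seen late in a window after a clear CT would still not enter the rate at that visit, but it would be counted in the cumulative rate.
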